1.0 Background and rationale

Cancer of the cervix is preventable but continues to cause the deaths of an estimated 275,000 women worldwide each year, more than 88 percent of them in developing countries. Vaccination against human papillomavirus (HPV), a means of primary prevention, has been shown to be over 90 percent effective in protecting against the lesions that lead to the majority of cervical cancer cases, but only if administered before viral infection,^{2,3} which occurs soon after initiation of sexual activity.⁴ Secondary prevention is accomplished with cervical screening followed by treatment of precancer and is essential for protecting women who have been sexually active. The World Health Organization recently declared that "screening for cervical cancer once, at age 40, followed by removal of any discerned precancerous lesion" is a "best buy." Best buys are defined as actions that should be undertaken immediately to produce accelerated results in terms of lives saved, diseases prevented, and heavy costs avoided. Screening, with treatment when necessary, has been the key to the 70 percent or more reduction in cervical cancer cases in industrialized countries over the past 50 years, and it is critical to reducing the huge burden of cervical cancer in low-resource countries. Screening technologies appropriate to low-resource settings have advanced considerably in the past decade, but a key component of any effective screening strategy is treatment and treatment technologies have lagged behind. Treatment methods for developing countries must be low-cost, effective, and adaptable for areas with limited resources in terms of infrastructure and health care providers.

Cryotherapy, the current gold standard for treatment of precancerous cervical lesions in low resource settings,⁶⁻⁹ has many appealing features; however, in recent years a number of issues—particularly the use of compressed gas, which requires storage and replenishment of large and potentially dangerous tanks—have emerged as clear limitations.

Two technologies—the CryoPen[®], manufactured and sold by CryoPen[®], Inc. (TX, USA), and the cold coagulator commercialized by WISAP Medical Technology (Germany) are treatment options for precancerous cervical lesions that run on electricity and avoid the difficulties associated with compressed gas. The CryoPen[®] is a treatment option for precancerous cervical lesions that are able to meet core criteria of cost, safety, and potential for use in remote campaign locations as well as in clinic settings. The CryoPen[®] differs from previous cryotherapy methods in that it does not require an external source of gas (a tank), since the gas for cooling is built into the system. The original device has been redesigned to be portable, durable, low-cost and low-maintenance for use in low-and middle-income countries (LMICs).

Cold coagulation ("thermocoagulation") has been used since the 1970s for treatment of cervical lesions. In spite of its name, this is treatment with a probe heated to temperatures of 100 to 120°C. Henceforth this treatment method will be referred to as "thermoablation." It is also an effective, inexpensive method that does not require high-level healthcare providers.

The purpose of this study is to conduct a randomized non-inferiority clinical trial to compare the LMIC-adapted CryoPen[®] and WISAP C3 thermoablator to CO₂-based cryotherapy for the treatment of CIN2 or more severe diagnoses ("CIN2+") but excluding microinvasive or invasive cervical cancer.

2.0 Study objectives

The primary objective of the study is to compare CIN2+ cure rates at twelve-months post-treatment with the LMIC-adapted CryoPen[®], the WISAP thermoablator, and CO₂-based cryotherapy.

Secondary objectives of the study are:

- To measure patient acceptability of the CryoPen® and thermoablator with pain scores and surveys
- To actively assess side effects of cryotherapy and thermoablation including infection, pain, bleeding, discharge, and stenosis at a six-week post-treatment visit
- To evaluate the sensitivity of high-risk HPV DNA testing post-ablation

3.0 Study design and statistical analysis

3.1 Study design

Women will be recruited from the Salvadorian Social Security Hospital (ISSS) in San Salvador, El Salvador, Hospital Universitario San Ignacio (HUSI) and Ginesalud SAS in Bogota, Colombia and Shanxi Bethune Hospital – Shanxi Academy of Medical Sciences (SBH) in Taiyuan, China. Women attending a regional screening program will also be recruited at three hospitals in Xinxiang, Henan Province, China: Yanjin County Women and Children Hospital, Fengqiu County Women and Children Hospital, and Weihui Municipal Hospital for Women and Children Healthcare.

All hospitals are referral sites for women with abnormal cytology.

Eligible women will be those over the age of 18 with biopsy results of CIN2+ (high grade CIN not otherwise specified) who consent to participate after being informed about the study and are willing and able to provide a permanent and reliable address. Women will be excluded if they are pregnant or plan to become pregnant during the study, have had previous surgery destructive to the cervix in the last 5 years, or have a history of total hysterectomy.

Women who meet the eligibility criteria listed above, will be invited to participate in the study. The diagnosis of CIN2+ will be based on the local pathology diagnosis.

Women will be randomly assigned to one of three study arms:

- A. CO₂-based cryotherapy (double freeze)
- B. LMIC-adapted CryoPen® (single freeze)
- C. Thermoablation for 40 seconds at 100°C followed by additional 20-second applications if necessary according to clinician's criteria in order to fully ablate the squamo-columnar junction (SCJ).

Women with CIN2+ (1.602)

Ineligible/No Consent

Local Standard of Care

Yes (1.152)
Randomizatio
n

WISAP
thermoablator

CO2-based cryotherapy

LMIC-adapted CryoPen

LEEP/CKC

12-month follow-up
(930)

VIA, cytology, HPV
testing, 4-quadrant biopay

CIN2/3

CIN2/3

Recruitment, enrollment, and patient flow are summarized in Figure 1.

Figure 1 Consort diagram of study patient flow

The single or double freeze modalities were chosen given the results of the UH2 trial where single-freeze CryoPen® achieved a greater depth of necrosis than double freeze, and the WHO cryotherapy guidelines which endorse CO₂ double-freeze as the standard cryotherapy treatment. While these are the preferred modalities, in a few cases clinicians may decide to repeat the CryoPen® modality to correct placement of the first application and maximize treatment efficacy and patient safety.

We will approach approximately 1,602 women with CIN2+ during a 2.5 year enrollment phase (30 months). Assuming an approximately 80% participation rate, ¹⁰ approximately 1,281 women will be enrolled—1,152 (90%) will be eligible for cryotherapy (i.e. no contraindications) and 129 will be ineligible and undergo alternative treatments. We estimate that approximately 20% will be lost to follow-up at the twelve-month visit, so that we will have complete data on a total of 922 women (57.5% of 1,602) treated with either CO₂-based cryotherapy, LMIC-adapted CryoPen®, or thermoablation. We will monitor the percentages of ineligibles, contraindications, and loss to follow-up in real time and adjust recruitment accordingly to achieve the target sample size. In addition, we will conduct a non-essential 6-week follow-up visit to evaluate adverse effects from the ablative procedures. The primary endpoint of the study will be to determine residual disease at a 12-month follow up visit as determined by colposcopy and four-quadrant biopsies.

Enrollment and Treatment

Enrollment diagnosis will be based on the local pathology. These slides will be read by an expert gynecologic pathologist for quality assurance. At the pre-treatment visit, consented women will be administered a short questionnaire to collect demographic

information and health history. Women will receive a pregnancy test as part of the eligibility criteria for enrollment in the study. Vaginal samples will be collected to be analyzed for bacterial vaginosis, yeast, gonorrhea, trichomonas, and chlamydia. Samples will be collected again at the 6-week follow-up visit to conduct the same analyses. Pathology samples from Latin America will be sent to the Pathology Department at the Medical College of Wisconsin (Milwaukee, WI) for molecular analyses. The China samples will be analyzed in-country at both SDH and Hybribrio labs using molecular tests as well. In addition, the ability to pass the cervical swab used for vaginal samples into the endocervix will be recorded at both the pre-treatment and the six-week follow-up visits to gather information about treatment-induced stenosis. All women will also undergo HPV genotyping with next-generation sequencing. The specimen is taken prior to treatment to establish a baseline of which HPV types are present. If a different HPV type is present in the post-treatment specimen, this will be classified as a new rather than persistent infection. Evaluation of the HPV genotyping from Latin America will be conducted at the National Cancer Institute in the United States and in China, where these samples will be analyzed at local labs. All samples that are sent to the United States for analysis will be shipped using a specialized courier service.

All women will also undergo a pelvic exam and visual inspection of the cervix following placement of diluted acetic acid on the cervix. Women will be immediately withdrawn from the study if any of the following contraindications for cryotherapy are present on visual inspection 1) lesion extends to over 75% of the cervix, 2) lesion is too large to be covered by the cryotherapy probe, 3) lesion extends into the endocervical canal, 4) the cervix is distorted or has severe atrophy; 5) the cervix is not visible, 6) the squamo-columnar junction is not completely visible, 7) the cervix is hard to reach, and/or 8) suspicion of cancer. Women deemed ineligible for cryotherapy will undergo LEEP immediately. In the case of suspected cancer, women will be appropriately referred. Once a patient is deemed eligible for cryotherapy, the study coordinator at each site will log into REDCap (a secure, HIPAA-compliant web application for building and managing surveys and databases) to obtain the randomized treatment assignment.

Women will then undergo treatment with the LMIC-adapted CryoPen[®], the WISAP thermoablator, or CO₂-based cryotherapy. Patient pain will be evaluated four times during the treatment visit as described in section 5.2 below.

Images of the cervix will be taken with the EVA System Mobile ODT device before and after treatment. De-identified cervical images from the initial visit and the follow-ups will be made available to Mobile ODT. The company will use these images to help develop an Automated Evaluated System (AVE), a software algorithm to detect pre-cancerous lesions through images rather than laboratory tests. This algorithm is currently in development and the more images it "learns", the more accurate results it can obtain. If successful, AVE can greatly ease diagnosis and triage in low-income settings.

Six-week follow-up

Six weeks post-treatment, women will return for a visit to evaluate side-effects. Data will be collected on women who attend this visit at any time between 4 to 12 weeks post-treatment. If a woman does not attend this visit, she will still remain in the study and be invited to return at 12 months post-treatment. At the 6-week visit, women will complete a questionnaire to assess the presence of pain or cramps, bleeding, watery discharge, and malodorous discharge. Women will also be asked some questions about their attitudes and perceived acceptability of the treatment they received. Finally, women will be asked to answer a checklist to assess their compliance with post-treatment recommendations. In addition, a pelvic exam will be performed and vaginal samples will be collected and analyzed for bacterial vaginosis, yeast, gonorrhea, trichomonas, and chlamydia. If an infection is suspected, the provider may prescribe medication as necessary. The provider will note whether a vaginal culture swab can be introduced into the endocervix. If it cannot, stenosis will be diagnosed. Women will also be evaluated for acute clinical cervicitis at the follow-up visit and this will be recorded. Another photo will be taken with the Mobile ODT device.

12-month follow-up

One year post-treatment, women will return for a follow-up visit to determine residual disease, which is the primary endpoint. Residual disease will be determined by colposcopy and four-quadrant biopsies. In addition, VIA, cytology, and high-risk HPV DNA testing with careHPV will be performed. Genotyping and next-generation sequencing will be repeated to differentiate between persistent and new infections. The goal is to evaluate which test has the highest sensitivity after an ablative treatment: VIA, cytology, or HPV.

We will use local health systems, including healthcare promoters, to encourage women to return for the follow-up visit. Attempts to contact women who do not return for this visit will continue until 18 months post-treatment. If a woman does not return within this time period, she will be considered lost to follow-up.

At the 12-month visit, the following procedures will be performed:

- 1. Pelvic examination
- 2. Urine pregnancy test
- 3. Unaided VIA
- 4. Cytology
- 5. High-risk HPV testing with careHPV
- 6. Colposcopic evaluation and impression
- 7. Four-quadrant microbiopsy protocol using the protocol for sensitive detection of any recurrent/untreated CIN2+.¹¹ All visible lesions in each quadrant of the cervix (12-3, 3-6, 6-9, and 9-12 o'clock) will be biopsied. Endocervical curettage (ECC) will be performed on all patients. If no lesion is visible in a given quadrant, the most suspicious appearing area in that quadrant will be biopsied.
- 8. Cervical swab collection for HPV genotyping using next-generation sequencing (NGS)

Treatment acceptability questions will again be administered at the end of this visit. Women diagnosed with recurrent/untreated CIN2+ on biopsy will be asked to return to undergo LEEP. Women with suspected cancer on biopsy will be referred to the local cancer hospital for standard of care.

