3.2 Sample size and statistical analyses

Treatment efficacy

Analytic Approach. The primary analysis will follow an "intent to treat" approach, and we will conduct an additional sub-analysis excluding patients referred to excisional treatments after randomization. Similarity of the two study arms in terms of follow-up rates, distribution of individual and demographic variables, and disease distributions will be assessed. We will calculate the cure fraction and the corresponding binomial 95% confidence interval (95% CI) of each treatment as the percentage of women diagnosed with CIN2+ at the twelve-month visit. The non-inferiority of the LMIC-adapted CryoPen[®] and the WISAP thermoablator relative to CO₂-based cryotherapy will be assessed by calculating 95% CIs for the differences (LMIC-adapted CryoPen® minus CO₂-based cryotherapy and WISAP thermoablator minus CO₂-based cryotherapy) in cure fractions. Non-inferiority will be concluded if the lower confidence bound is greater than the non-inferiority margin (-10%). Exploratory analysis of the effectiveness and differences between arms will be evaluated within strata defined by quartiles of age and by the baseline diagnosis. Both the local and expert pathologists' diagnoses will be used in these analyses. As warranted, a logistic regression model will be used to mutually control for all important variables and chance differences between study arms to identify the key determinants of treatment failure and differences (if any) in effectiveness between treatments.

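### The primary analysis is called intent-to-treat but is most likely a completers' analysis: about 20% of randomised women are expected to have no outcome, and no rule or sensitivity analysis covers them.

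*Combined protocol and SAP*

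**What the plan says.** Section 3.2 (Treatment efficacy, Analytic Approach) states: "The primary analysis will follow an 'intent to treat' approach". It defines neither the analysis set nor the denominator. It bases the cure fraction on the "percentage of women diagnosed with CIN2+ at the twelve-month visit". Non-inferiority is declared when the lower 95% confidence bound for device minus CO₂ cryotherapy lies above -10 points.

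Section 3.1 defines the outcome by attendance: "The primary endpoint of the study will be to determine residual disease at a 12-month follow up visit", established by colposcopy and four-quadrant biopsies. The expected flow is "approximately 1,281 women will be enrolled—1,152 (90%) will be eligible for cryotherapy". Attrition comes next: "We estimate that approximately 20% will be lost to follow-up at the twelve-month visit". The plan then counts on the women who remain: "so that we will have complete data on a total of 922 women". Contact attempts continue to 18 months, and then: "If a woman does not return within this time period, she will be considered lost to follow-up". No outcome is attached to that status.

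Section 3.2 (Statistical Power and Sample Size) bases power on the 922 women, 307 per arm.

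Three other items in section 3.2 come near the issue:
- a comparison of follow-up rates between arms, with no action attached;
- a secondary analysis that drops women sent for excision once randomised;
- a logistic regression to be used if warranted, which still needs an observed outcome.

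**The concern.** An analysis by assigned arm keeps the protection of randomisation only if every randomised woman contributes, or if those who do not are missing for reasons that do not distort the comparison. Here about one woman in five is expected to contribute nothing, and the plan neither says how she is handled nor checks whether her absence matters.

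In a non-inferiority trial, anything that moves an unfavourable difference towards zero favours the new device. If women whose treatment failed are less likely to return in a device arm than in the control arm, the completers' difference looks better than the true one. With no rule written down, the handling could also be chosen after the data are seen.

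**Working it through.** **Inputs.** Section 3.1: 1,602 approached, 80% participation, 90% eligible, 20% lost. Section 3.2: 307 per arm, margin 10 points, 95% CI, control cure 50% to 80%. Assumptions not in the documents: the difference in cure between lost women and returners; equal 20% loss in each arm; and cured meaning no CIN2+ found.

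**1. The plan's own figures.** 1,602 × 0.80 = 1,281.6; 1,281 × 0.90 = 1,152.9; 1,152 × 0.80 = 921.6, so 922. Per arm, 1,152 / 3 = 384 randomised and 922 / 3 = 307 with data. At 307 per arm, control cure 50% and one-sided 5%, power is Φ(0.10 / √(2 × 0.25 / 307) − 1.645) = Φ(2.478 − 1.645) = 79.8%, which matches the stated 80%. The inflation for loss is correct, and the power is that of a completers' analysis. Women without an outcome: 1,152 − 922 = 230, about 77 per arm.

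**2. Bias among completers.** Let g be the amount by which cure in lost women falls below cure in returners. With 20% lost, cure in returners = cure in all randomised + 0.2 × g. Therefore:

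observed difference = true difference + 0.2 × (g in device arm − g in control arm).

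Only the difference between the two gaps matters. If they are equal, the bias is zero. If only control has a gap, the bias runs against the device.

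**3. Size under a gap in the device arm only.** True difference -10 points, control 70%, device 60%, n = 307. P(false non-inferiority) = Φ((observed difference + 0.10) / SE − 1.96).

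- g = 10 points: device returners 62%, observed -8. SE = √((0.62 × 0.38 + 0.70 × 0.30) / 307) = 0.0381. Φ(0.525 − 1.96) = 7.6%.
- g = 20 points: device returners 64%, observed -6. SE = 0.0379. Φ(1.056 − 1.96) = 18.3%.
- g equal in both arms: observed -10, error 2.5%.

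For control cure of 50% and 80%, the results are 7.2% and 8.4% (g = 10) and 16.7% and 21.8% (g = 20). With a one-sided 5% bound, the 70% case gives 13.1% and 27.8% against 5%.

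**4. Setting every lost woman to one value.** With 384 per arm and equal 20% loss, take a difference of -10 among returners. Cure becomes 0.8p + 0.2 (all cured) or 0.8p (all failed). Either way the difference becomes 0.8 × (-10) = -8.

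| Control cure | Lost = cured | Lost = failed |
|---|---|---|
| 50% | 8.1% | 8.4% |
| 70% | 9.0% | 8.0% |
| 80% | 10.3% | 8.2% |

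All entries compare with 2.5%.

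**5. What a tipping-point analysis would show.** Suppose the completers' difference is exactly zero at control 70%. The lower bound is -1.96 × √(2 × 0.21 / 307) = -7.25 points, which leaves 2.75 points of room. An excess gap of 2.75 / 0.2 = 13.75 points in the device arm would bring the bound to about -10, if the interval width is held fixed.

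**The case against.** A reader might infer a stronger reading: that the intent-to-treat label promises a denominator of 1,152, so that lost women, having no CIN2+ diagnosis, are counted as cured and the error rate becomes 8% to 10%. The documents do not support that. The label appears next to a secondary analysis that drops women sent for excision, so in context it mainly means keeping women in their assigned arm. All the planning counts women with 12-month data, and nowhere is a non-returner given an outcome. The reading also needs a silent correction, because section 3.2 literally equates the cure fraction with the percentage who have CIN2+. The defect is an undefined analysis set and not a broken promise.

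The completers' figures can also be challenged. They rest on a gap in one arm only, which nothing in the documents indicates. The planned six-week visit assesses side effects and not cure, so study procedures would not tell a woman her cure status before she decides whether to return. That makes outcome-related loss that differs by arm less likely, though not impossible. Nor does a missing share of 20%, twice the margin, measure bias by itself.

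The plan does work to limit loss: contact to 18 months, real-time monitoring with recruitment adjusted, and part of site payment held until follow-up is complete. These steps may reduce the number missing and restore precision. They do not show whether the remaining loss is related to outcome.

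Finally, multiple imputation corrects only what its covariates explain. The six-week visit is optional, includes no histology or HPV test, and may be missed by the same women. This objection stands, and it determines where the weight of the fix should fall.

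**Conclusion.** The point holds as a gap in the analysis plan. The sample-size arithmetic is correct. The primary comparison is most likely one of completers, with about 230 of 1,152 randomised women left out and no check on whether their absence favours a device.

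The 8% and 18% false non-inferiority rates are illustrations and not predictions. They assume equal 20% loss, a gap of 10 or 20 points in the device arm only, control cure 70%, a true difference of exactly -10 points, and the lower limit of a two-sided 95% interval. With no gap, or equal gaps, the error stays at 2.5%. The result that all-cured and all-failed both shrink -10 to -8 holds for equal loss; unequal loss can move the difference in either direction.

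The change should be made because the primary conclusion depends on it and the cost is small.

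**What to change.** In section 3.2, Treatment efficacy, Analytic Approach:

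- Define the primary analysis set as all randomised women, by assigned arm.
- Estimate each difference in cure fractions by multiple imputation within arm, using site, age, baseline grade, baseline HPV genotype and six-week findings where available.
- State that a missing 12-month outcome is not deterministically set to cured or to failed. Imputation will still draw cured for some lost women, as it should.
- Report the completers' analysis as supporting.
- Add a tipping-point analysis for each device, showing how much lower cure among lost device-arm women must be, relative to control, before the lower bound crosses -10%.

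The cost is SAP text and programming, with possibly slightly wider intervals. No visits, procedures or participants are added. If the covariates predict outcome weakly, the imputed estimate may lie close to the completers' one, so the tipping-point analysis is the main protection.

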Statistical Power and Sample Size. With a total of 922 women with a diagnosis of CIN2+, 307 per treatment arm, the study will have at least 80% power (alpha = 0.05) to detect a non-inferiority margin difference of 10% between the cure fraction of CO₂-based cryotherapy (reference) and of the LMIC-adapted CryoPen® (experimental) and the WISAP thermoablator (experimental), for a range of efficacy (50% to 80%) for the reference treatment and 40% efficacy under the null hypothesis of inferiority. We chose a range of 50-80% efficacy for cryotherapy because although the literature suggests CO₂-based cryotherapy is 80% effective, the disease ascertainment by colposcopy following treatment in previous studies was before the recognition that colposcopy is not perfectly sensitive. Therefore, the disease ascertainment in those studies was not as rigorous as proposed in this study. To ensure that the study is sufficiently powered for a wide range of efficacies, we are selecting 50% efficacy for the control arm as the worst-case scenario for study power. In order to achieve a sample size of 922 with complete follow-up, we will enroll 1281 women with CIN2+ under the assumption that 10% will have contraindications for cryotherapy and 20% will be lost to follow-up at twelve months post-treatment.

Test of cure

Analytic Approach. Since all women returning for the twelve-month visit will undergo four-quadrant biopsies and LEEP if diagnosed with CIN2+, regardless of the baseline characteristics or ablative treatment, we can assess the test of cure performance (sensitivity, specificity, positive predictive values (PPV), and negative predictive values (NPV)) of each test (VIA, cytology, and high-risk HPV DNA) for recurrent CIN2+ and CIN3 diagnosed by local and expert pathology. Performance will be stratified by quartiles of age and by the baseline diagnosis. McNemar chi-square will be used to test whether differences in sensitivity and specificity are significant (p < 0.05). A method developed by Leisenring *et al.* ¹² will be used to test for significant differences in PPV and NPV.

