Statistical Power. The statistical power for comparing sensitivity for the test of cure for VIA, cytology, and high-risk HPV testing is dependent on sample size of the efficacy study and the actual efficacy. We are enrolling 1281 women to assure that we have 930 women with a twelve-month follow-up. The larger the number of women who return for their follow-up, the larger the sample size for a given level of efficacy will be. The more efficacious the treatments, the smaller the sample size will be. Assuming 70% efficacy in treatment (30% recurrence), results of tests for cure will be available for 279 women with recurrence. This will provide 85% power (0.05 two-sided alpha) to detect a 10% difference in sensitivity between tests assuming 20% discordance between tests.

Interim Analysis of Cure Fractions. An interim analysis of cure fractions will be performed after approximately 2 years of study opening, when approximately 1/3 of the women have been enrolled. A confidence interval will be calculated for the difference (LMIC-adapted CryoPen® minus CO₂-based cryotherapy and WISAP thermoablator minus CO₂-based cryotherapy) in cure fractions. If the upper bound of the confidence interval is lower than the non-inferiority margin (-10%), then treatment modification or termination may be considered. The confidence interval will be calculated using an alpha calculated using an alpha time-squared spending function to maintain an overall 5% Type I error (one-sided).

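### The 12-month biopsy sampling rests partly on an examiner whom the plan neither identifies nor keeps unaware of the device, so arm-dependent sampling could bias the cure difference in either direction

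*Combined protocol and SAP*

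**What the plan says.** Section 3.1 (12-month follow-up) defines how the endpoint is ascertained: "Residual disease will be determined by colposcopy and four-quadrant biopsies". Item 7 of its procedure list sets the sampling rule. Every lesion seen in a quadrant is biopsied, with no upper limit, and ECC is done in all women. For the remaining quadrants, "If no lesion is visible in a given quadrant, the most suspicious appearing area in that quadrant will be biopsied". The colposcopic impression is item 6, just before sampling.

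On knowledge of the arm, section 3.1 (Enrollment and Treatment) says that, once a woman is found eligible, "the study coordinator at each site will log into REDCap" to obtain the assignment. The protocol text does not say who carries out the 12-month examination, whether the treating clinician may do so, or whether the arm is hidden from the examiner.

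The one stated protection against biased cure rates is in section 5.3: local and expert pathologists reach consensus, with a third reader if needed. That section calls the endpoint tissue colposcopy-directed biopsies, whereas section 3.1 specifies four-quadrant biopsies. The two descriptions should be reconciled.

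**The concern.** Detection of residual CIN2+ has two steps: taking the right tissue and reading it correctly. The plan protects the second by consensus. The first depends partly on the eye of one person, and section 3.2 itself accepts that colposcopy misses disease. If that person knows the device, expectations about it could affect what is called a lesion, how many biopsies exceed four, and which spot is chosen in a quadrant without a lesion.

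A missed case counts as a cure. Less thorough sampling in a device arm makes that device look better and raises the chance of a false non-inferiority claim. More thorough sampling in a device arm makes it look worse and costs power. No consensus of pathologists, masked or not, can correct either, because the missing tissue never reaches them.

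**Working it through.** **1. The plan's own figure.** Section 3.2 states "With a total of 922 women with a diagnosis of CIN2+, 307 per treatment arm", and that "the study will have at least 80% power (alpha = 0.05") for a 10-point margin, with 50% control cure as the worst case. With equal true cure, power = Φ(0.10/SE − z), where SE = √(2 × 0.5 × 0.5/307) = 0.0404.
- One-sided 0.05: Φ(2.478 − 1.645) = 79.8%. The stated 80% is reproduced.
- One-sided 0.025: Φ(2.478 − 1.960) = 69.8%.

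For the decision rule, section 3.2 says non-inferiority "will be assessed by calculating 95% CIs for the differences". I read these as two-sided intervals, so each claim is tested at one-sided 0.025.

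**2. Inputs.**
- From section 3.2: 307 per arm; margin −10 points; 30% recurrence, the figure used there for the test-of-cure power and taken here as true CO₂ failure.
- By construction: true device failure of 40%, exactly at the margin, so every non-inferiority claim is false.
- Assumed: the share of true failures detected in each arm. The documents give no figure, so a range is shown.

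**3. Formula.** Observed failure = true failure × detection. Let D be observed device failure minus observed CO₂ failure, and SE = √[(f_C(1 − f_C) + f_D(1 − f_D))/307], with f_C and f_D the observed failure proportions. Then P(claim) = Φ((0.10 − D)/SE − 1.96).

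Example, 90% CO₂ and 85% device: f_C = 0.30 × 0.90 = 0.27; f_D = 0.40 × 0.85 = 0.34; D = 0.07; SE = 0.0371; Φ(0.03/0.0371 − 1.96) = Φ(−1.150) = 12.5%.

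| Detection CO₂ / device | f_C / f_D | Cure difference seen | SE | False claim rate |
|---|---|---|---|---|
| 100% / 100% | 0.300 / 0.400 | −10.0 | 0.0383 | 2.5% |
| 90% / 90% | 0.270 / 0.360 | −9.0 | 0.0373 | 4.5% |
| 90% / 89% | 0.270 / 0.356 | −8.6 | 0.0373 | 5.7% |
| 90% / 88% | 0.270 / 0.352 | −8.2 | 0.0372 | 7.0% |
| 90% / 85% | 0.270 / 0.340 | −7.0 | 0.0371 | 12.5% |
| 90% / 80% | 0.270 / 0.320 | −5.0 | 0.0368 | 27.4% |
| 85% / 90% | 0.255 / 0.360 | −10.5 | 0.0370 | 1.8% |

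The rise from 2.5% to 4.5% comes from detection that is imperfect but equal. Masking would not change that part, so the effect of arm-dependent sampling is measured from 4.5%. A 5-point gap is about 6 extra missed cases (0.05 × 122.8) among 307 × 0.40 = 122.8 true failures.

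**4. Other cure rates and the other alpha.** For device detection of 90%, 88%, 85% and 80% against 90% for CO₂:
- control cure 50%: 4.4%, 7.9%, 16.7%, 41.3%;
- control cure 80%: 4.8%, 6.9%, 11.4%, 23.0%;
- control cure 70% at one-sided 0.05: 8.4%, 12.3%, 20.2%, 38.8%.

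**5. The opposite direction.** Take truly equal devices at 50% cure, with 90% detection under CO₂ and 100% in the device arm. Observed cure is 0.55 against 0.50, a difference of −0.05, with SE = √((0.2475 + 0.25)/307) = 0.0403. Power is Φ(0.05/0.0403 − 1.96) = 23.6%, against 69.8% with perfect detection in both arms.

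**The case against.** The strongest reply is that the examiner's discretion is small. Four quadrant biopsies plus ECC are mandatory, and a quadrant that looks normal is still sampled. This stands and bounds the bias: what remains open is recognising a lesion, the spot within a quadrant, and the count above four. The protocol also follows a cited four-quadrant method that may add rules; it could not be checked here.

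A reader might infer that the clinician who treated the woman, knowing the device, also samples her at 12 months. The documents do not support that. They say that the coordinator obtains the assignment. Section 6.0 states that the coordinator is not the woman's primary doctor, and section 12.0 gives coordinators recruitment, consent and interviews. Who examines at 12 months is simply not stated.

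A reader might also infer that the gap favours the new devices. Nothing in the documents says so. An examiner wary of a new device might sample it harder, and the table shows that the false claim rate then falls. Small gaps have modest effects: one point moves the rate from 4.5% to 5.7%.

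Finally, the visit already includes cytology, careHPV and genotyping for every woman. These do not replace the endpoint, but they offer a check on under-sampling that the plan does not yet use.

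**Conclusion.** The point holds in a limited form. Part of the endpoint sampling depends on the judgement of an examiner whom the plan neither identifies nor keeps unaware of the arm, and the only stated safeguard acts after the tissue is taken. The direction and size of any bias are unknown. In the main scenario (70% control cure, device truly at the margin, two-sided 95% interval), device detection 2 to 10 points lower raises the false non-inferiority rate from 4.5% to between 7.0% and 27.4%. Detection 5 points lower under CO₂ reduces it to 1.8%. These figures illustrate sensitivity under assumed detection rates. They do not show that sampling will differ by arm or that non-inferiority would be falsely declared. The point is a cheap improvement to how the primary endpoint is ascertained.

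**What to change.** In the 12-month follow-up part of section 3.1:

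1. State who performs the examination. Hide the arm and the treatment record from the 12-month REDCap form and from the examiner until the biopsies and ECC are logged, with earlier access if care requires it.
2. Where a site already has two study providers, schedule the one who did not treat the woman.
3. Record the number and quadrant of biopsies and tabulate them by arm. Beside them, tabulate by arm the HPV and cytology positivity among biopsy-negative women. An imbalance would be a signal of differential under-sampling, not a correction for it, because the devices may also differ in viral clearance.

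A sensitivity analysis restricted to one biopsy per quadrant plus ECC is not advised. The same examiner still chooses the spot, and discarding tissue lowers detection in both arms. At 80% detection in each, f_C = 0.24, f_D = 0.32 and SE = 0.0361, so the false claim rate is Φ(0.02/0.0361 − 1.96) = 8.0%, against 4.5% at 90% in each.

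The cost is a REDCap display setting, some scheduling among existing staff and a few tables. The downside is that the examiner normally sees the treatment record only after sampling. If examiners are already masked in practice, one sentence settles item 1.
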